10.3.4. Treatment IV: Deep and Shallow Injections, 5 Aliquots

In Treatment IV, study drug will be injected subcutaneously using a 3 mL syringe with 0.1 mL gradients and a 30-gauge 1-inch needle, while the subject lies in a prone position. Each injection will consist of a single skin injection of study drug administered as five 0.3 mL aliquots to Position A, B, C, D and E (for a total injection volume of 1.5 mL) as shown in Figure 4. The depth of injection for Position A corresponds to the length of the treatment needle (1 inch) from the tip of needle to the hub or base of needle without downward pressure, and for the rest of the Positions (B to E), the length of the treatment needle corresponds from the tip of the needle to approximately one half (1/2 inch) of the needle length.

During each treatment visit, 24 syringes (12 syringes per treatment area) will be prepared for dosing. Each syringe will contain 1.5 mL of study drug (5 aliquots of 0.3 mL, for each injection, in each syringe).

Figure 4: Treatment IV: Deep and Shallow Injections, 5 Aliquots

- With the needle positioned at an angle of approximately 30° to the skin surface at the injection site and directed towards subject's head, push the needle all the way in (1 inch) and inject 0.3 mL of study drug by gently pushing the syringe plunger.
- Gently withdraw half the length of the needle (1/2 inch), maintaining the 30° angle of the needle to skin surface, and reposition it towards one side of the subject (Position B). Inject 0.3 mL study drug by gently pushing the syringe plunger.
- Maintain the 30° angle of the needle to the skin surface, reposition the needle to midway between Position A and B (Position C, towards subject's shoulder) and inject 0.3 mL of study drug by gently pushing the syringe plunger.

[figure not shown]
- Maintain the 30° angle of the needle to the skin surface, reposition the needle exactly opposite to Position B (Position D), and inject 0.3 mL of study drug by gently pushing the syringe plunger.
- Maintain the 30° angle of the needle to the skin surface, reposition the needle to midway between Position A and D (Position E, towards subject's other shoulder) and inject 0.3 mL of study drug by gently pushing the syringe plunger.
- A 3 mL syringe with 1.5 mL of study drug will be sufficient for one injection site.
- Use twelve (12) 3 mL syringes in each treatment area (each buttock or each thigh) to administer a total of 12 injections of 1.5 mL (total of 18.0 mL, 5 aliquots 0.3 mL each) at 12 injection sites.
- Discard the used needles and syringes.
- A total of 24 injections will be administered across the 2 treatment areas (2 buttocks or 2 thighs) at each treatment visit.

10.3.5. Treatment V: Shallow Injections, 4 Aliquots

Study drug will be injected subcutaneously using a 3 mL syringe with 0.1 mL gradients and a 30-gauge ½ -inch needle, while the subject lies in a prone position. Each injection will receive a single skin injection of study drug administered as four 0.3 mL aliquots to Position A, B, C and D (for a total injection volume of 1.2 mL) as shown in Figure 5. The depth of injection corresponds to the length of the treatment needle (1/2 inch) from the tip of the needle to the hub or base of the needle without downward pressure.

During each treatment visit, 24 syringes (12 syringes per treatment area) will be prepared for dosing. Each syringe will contain 1.2 mL of study drug (4 aliquots of 0.3 mL each).

Figure 5: Treatment V: Shallow Injections, 4 Aliquots

- With the needle positioned at an angle of approximately 30° to skin surface at the injection site and directed towards one side of the subject, push the needle all the way in (1/2 inch), and inject 0.3 mL of study drug by gently pushing the syringe plunger.

- Maintain the 30° angle of the needle to the skin surface, reposition the needle to approximately 60° from Position A and towards the subject's shoulder (Position B), and inject 0.3 mL of study drug by gently pushing the syringe plunger.
- Maintain the 30° angle of the needle to the skin surface, reposition the needle to approximately 60° from Position B and towards subjects other shoulder (Position C) and inject 0.3 mL of study drug by gently pushing the syringe plunger.
- Maintain the 30° angle of the needle to the skin surface, reposition the needle opposite to position A and towards other side of the subject (Position D) and inject 0.3 mL of study drug by gently pushing the syringe plunger.
- A 3 mL syringe with 1.2 mL of study drug will be sufficient for one injection site.
- Use twelve (12) 3 mL syringes (with 1.2 mL study drug in each) in each treatment area (each buttock or each thigh) to administer a total of 12 injections of 1.2 mL each (total of 14.4 mL, 4 aliquots of 0.3 mL each) at 12 injection sites.
- Discard the used needle and syringes.
- A total of 24 injections will be administered across 2 treatment areas.

10.3.6. Care Procedures After Injection

NOTE: CCH is a foreign protein and Investigators should be prepared to address and manage an allergic reaction should it occur. At the time of each injection, a 1:1,000 solution of epinephrine for injection, 50-mg diphenhydramine injection or a suitable equivalent, and oxygen must be available with the Investigator and site staff must be familiar with their use. To evaluate the subject for possible immediate immunological AEs, the subject will remain in direct observation of medical personnel who are skilled in the management of an allergic reaction for 30 minutes after receiving the injections of study drug and until the subject exhibits no sign of an immunological or other clinically significant systemic or local AE. The subject's vital signs should be stable before the subject can leave direct observation.

The Investigator or qualified designee will then apply a sterile dressing to the injection areas with hypoallergenic tape. The subject will be instructed to remove the dressing in the evening.

10.4. Discussion of Study Design, Including the Choice of Control Groups

This is an exploratory study to assess the safety and treatment effect of different injection techniques of CCH for the treatment of EFP. The study will also explore the use of 3-D photography in assessing outcomes in EFP. No control groups will be employed.

11. SELECTION AND WITHDRAWAL OF SUBJECTS

11.1. Subject Inclusion Criteria

No subject will be assigned to treatment until all eligibility criteria have been satisfied. To qualify for the study a subject must:

1. Be able to provide voluntary written informed consent prior to the initiation of any study-specific procedures per the policy of the governing Institutional Review Board (IRB)/Independent Ethics Committee (IEC).
2. Be female and at least 18 years of age at the time of consent.
3. Have evidence of cellulite in 2 bilateral treatment areas (defined as right and left buttocks OR right and left posterolateral thighs) as assessed by the Investigator at the Screening visit, and fulfills the following requirements:
 - a. has a score of 2 (mild), 3 (moderate) or 4 (severe) as reported by the Investigator (CR-PCSS) in 2 treatment areas (two thighs or two buttocks) at the Screening Visit.
 - b. has at least 2 dimples from each treatment area that:
 - are isolated and separated by at least 5 cm from any other dimples.
 - score 2 or 3 on the Hexsel depression scale.
 - have dimple width: length ratio ≥ 0.5 .
4. Be willing to apply sunscreen to the dosing areas before each exposure to the sun while participating in the study (ie, screening through end of study).
5. Be judged to be in good health, based upon the results of a medical history, physical examination, and laboratory profile at screening.
6. Have a negative serum pregnancy test at the Screening Visit and negative urine pregnancy at Day 1 (before injection of study drug), be using an effective contraception method (eg, abstinence, intrauterine device, hormonal [estrogen/progestin] contraceptives, or double barrier control) for at least 1 menstrual cycle prior to study enrollment and through Day 71 ; or be menopausal defined as at least 12 months of amenorrhea in the absence of other biological or physiological causes (as determined by the Investigator), or be postmenopausal for at least 1 year, or be surgically sterile (hysterectomy, bilateral oophorectomy, bilateral tubal ligation).
7. Be willing and able to comply with all protocol required study visits and assessments.

11.2. Subject Exclusion Criteria

A subject who meets any of the following criteria will be excluded from the study:

1. Is pregnant or is intending to become pregnant during the study.
2. Is presently nursing/breastfeeding or providing breast milk.
3. Has any of the following systemic conditions:
 - a. Coagulation disorder.

- b. Evidence or history of malignancy (other than excised basal-cell carcinoma) unless there has been no recurrence in at least 5 years.
 - c. History of keloidal scarring or abnormal wound healing.
 - d. Concurrent diseases or conditions that might interfere with the conduct of the study, confound the interpretation of the study results, or endanger the subject's well-being. Any questions about concurrent diseases should be discussed with the Medical Monitor.
 - e. Evidence of clinically significant abnormalities on physical examination, vital signs, electrocardiogram (ECG), or clinical laboratory values.
4. Has any of the following local conditions in the areas to be treated:
 - a. History of lower extremity thrombosis or post-thrombosis syndrome.
 - b. Vascular disorder (eg, varicose veins, telangiectasia).
 - c. Inflammation or active infection.
 - d. Severe skin laxity, flaccidity, and/or sagging.
 - e. Active cutaneous alteration including rash, eczema, psoriasis, or skin cancer.
 5. Has a tattoo located within 2 cm of the site of injection.
 6. Requires anticoagulant or antiplatelet medication during the study or has received anticoagulant or antiplatelet medication (except for ≤ 150 mg aspirin daily) within 7 days before injection of study drug.
 7. Has used any of the following for the treatment of EFP on the area to be treated within the timelines identified below or intends to use any of the following at any time during the course of the study:
 - a. Liposuction within the treatment areas during the 12-month period before injection of study drug.
 - b. Injections (eg, mesotherapy); radiofrequency device treatments; laser treatment; or surgery (including subcision and/or powered subcision) within the treatment areas during the 12-month period before injection of study drug.
 - c. Any investigational treatment for EFP/cellulite on treatment areas during the 12-month period before the injection of study drug.
 - d. Endermologie[®] or similar treatments within the treatment areas during the 6-month period before injection of study drug.
 - e. Massage therapy within the treatment areas during the 3-month period before injection of study drug.
 - f. Creams (eg, Celluvera[™], TriLastin[®]) to prevent or mitigate EFP within the treatment areas during the 2-week period before injection of study drug.
 8. Has received an investigational drug or treatment within 30 days before injection of study drug.
 9. Has a known systemic allergy to collagenase or any other excipient of study drug.

10. Has a history of drug or alcohol abuse.
11. Intends to initiate an intensive sport or exercise program during the study.
12. Intends to initiate a weight reduction program during the study.
13. Intends to use tanning spray or tanning booths during the study.
14. Has previously received any collagenase treatments (eg, Santyl[®] ointment and/or XIAFLEX/XIAPEX[®]).
15. Was a subject in a previous cellulite clinical trial of CCH: AUX-CC-830, AUX-CC-831, EN3835-102, EN3835-104, EN3835-201, EN3835-202, EN3835-205, EN3835-302, or EN3835-303.
16. Has any other condition(s) that, in the Investigator's opinion, might indicate the subject is unsuitable for the study.

11.3. Subject Discontinuation Criteria

A premature discontinuation will occur when a subject who signed informed consent ceases treatment and/or participation in the study, regardless of circumstances, prior to the completion of the protocol. Subjects can be prematurely discontinued from the study for any of the following reasons:

- An adverse event.
- A protocol violation (reason must be specified, for example: lack of compliance with protocol required study visits/assessments, use of a prohibited concomitant medication, etc).
- Withdrawal by subject (reason must be specified).
- The subject was "lost to follow-up".
- Other reasons (reason must be specified, for example: the subject moved, pregnancy, investigator decision, Sponsor decision to terminate trial, etc).

Subjects who discontinue, or are withdrawn from study treatment for any reason, will be encouraged to complete the remaining study visits and assessments and provide any additional follow-up information as required by the study, unless the subject specifically indicates that they will not participate in any further evaluations. The date a subject discontinues from the treatment and/or study and the reason for discontinuation will be recorded in the source documentation and Electronic Case Report Form (eCRF).

11.3.1. Replacement Procedures

Subjects who discontinue from treatment and/or who discontinue from the study will not be replaced.

12. TREATMENT OF SUBJECTS

12.1. Study Visits

The Schedule of Events to be performed at each study visit is shown in Section 5. Provided below are further details where additional instruction about the assessments that will be performed is deemed to be needed.

12.1.1. Subject Screening

Investigators will be expected to maintain a Screening Log of all potential study subjects. This log will include limited information about the potential subject and the date and outcome of the screening process (eg, enrolled into the study, reason for ineligibility, or refused to participate). Investigators will provide information about the study to subjects who appear to meet the criteria for participation in the study.

12.1.2. Screening Assessments

After obtaining informed consent, the full assessment of eligibility will be conducted and prior to study entry, screening assessments will be performed according to the schedule of events in Section 5.

12.1.3. Demographic Data

The following demographic information will be required for study entry:

- Date of birth.
- Gender.
- Race and ethnicity.

12.1.4. Medical/Surgical/EFP History

During the screening period, the Investigator or qualified designee will obtain a medical and surgical history from each subject that includes relevant diagnoses and/or procedures/therapies with onset/resolutions dates. Medical histories should also include history of EFP (start date, family history, and prior treatment), and history of tobacco and alcohol use (never, current, former).

12.2. Prior and Concomitant Medications and Procedures

All prior medications taken within 90 days before Day 1 will be recorded. All medications (including over-the-counter medications) taken by the subject on Day 1 through the end of the study must be recorded. In addition, all prior treatments (medications or procedures) for EFP must be recorded.

Additionally, any diagnostic, therapeutic or surgical procedures performed during the study period should be recorded including the date, indication for, and description of the procedure.

12.2.1. Prohibited Medications and Procedures

The following medications and procedures are prohibited for subjects during the study:

- Anticoagulants (warfarin, heparin, direct thrombin inhibitors, Factor X inhibitors) and antiplatelet agents (aspirin > 150 mg/day and P2Y12 inhibitors, such as clopidogrel), which can cause additional bruising. However, the use of aspirin at a dose level of ≤ 150 mg per day will be permitted during study.
- Liposuction within the treatment areas.
- Injections (eg, mesotherapy); radiofrequency device treatments; laser treatment; or surgery (including subcision and/or powered subcision) in the treatment areas.
- Any investigational treatment for EFP/cellulite on treatment areas or any other investigational drug or treatment.
- Endermologie or similar treatments within the treatment areas.
- Massage therapy within the treatment areas during the 3-month period before injection of study drug.
- Creams (eg, Celluvera, TriLastin) within the treatment areas.

12.3. Treatment Compliance

Subjects will receive study drug administered by the Investigator at the Investigator's site. Accidental or intentional overdoses should be reported to the Sponsor/designee promptly.

12.4. Blinding and Randomization

This study will be conducted as an open-label investigation; no blinding of assigned treatment will occur. Subjects will be sequentially assigned to Treatment Arms A to E at Day 1.

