5. SCHEDULE OF EVENTS

	Screening (Day-21 to Day -1)	Day 1	Day 4 (± 1 day)	Day 8 (± 1 day)	Day 15 (± 2 days)	Day 22 (± 2 days)	Day 43 (± 2 days)	End of Study/ Early Termination Day 71 (± 3 days)	Unscheduled Clinic Visit ^a
Procedures									
Informed consent ^b	X								
Inclusion/exclusion criteria review	X	X ^c							
Demographic data	X								
3-D Photography	X	X ^{d,e}	X	X	X	X ^{d,e}	X ^{d,e}	X	
Medical/surgical/EFP history (including previous treatment)	X								
Prior/concomitant medications/procedures	X	X ^c	X	X	X	X	X	X	X
Physical Examination	X							X	X
Height	X								
Weight	X	X ^e						X	X
Fitzpatrick skin type	X								
Vital signs	X	X ^f				X ^f	X ^f	X	X
12-lead ECG	X								
Clinical Laboratory Tests	X							X	X
Anti-AUX-I/anti-AUX-II antibody level sample		X ^e						X	
Serum pregnancy test	X								
Urine pregnancy test		X ^e				X ^e	X ^e	X	X
Assignment of treatment area (buttocks or thighs)	X								

	Screening (Day-21 to Day -1)	Day 1	Day 4 (± 1 day)	Day 8 (± 1 day)	Day 15 (± 2 days)	Day 22 (± 2 days)	Day 43 (± 2 days)	End of Study/ Early Termination Day 71 (± 3 days)	Unscheduled Clinic Visit ^h
Procedures									
Selection of 2 dimples within each treatment area for volumetric assessment	X	X ^e							
CR-PCSS	X								
Hexsel Depression Depth Scale	X					X	X	X	
Assign Treatment Arm (dosing injection technique)		X ^e							
Mark the dimple injection sites		X ^e				X ^e	X ^e		
Study drug administration		X				X	X		
Injection site reactions/local tolerability in the treated areas		X	X	X	X	X	X	X	X
All other adverse events					X				

^aDuring unscheduled visits the investigator or designee may perform any study procedure that they deem clinically necessary (eg, vital signs, clinical laboratory tests, pregnancy test, etc).

^bPerformed prior to any study-required assessments.

^cShould be reassessed and verified prior to study drug administration.

^dComplete before and after marking injection sites.

^eComplete prior to study drug administration.

^fVital signs will be collected up to 4 hours prior to, and at 15 and 30 minutes after study drug administration on Days 1, 22, and 43.

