12.5. Selecting and Marking Dimples

If all 4 quadrants (both buttocks and both thighs) meet entry criteria for a single subject, the thighs will be treated. No subject will have treatment in all 4 quadrants (both buttocks and both thighs) during this study.

Selection of dimples to be treated in the treatment areas (both buttocks or both thighs) is at the discretion of the investigator. Dimples must be well defined, evident when the subject is standing in a consistent, standardized relaxed pose (without the use of any manipulation such as skin pinching or muscle contraction), and suitable for treatment. Each subject will receive 3 treatment visits of study drug unless the treatment area is dimple-free at Day 22 and/or Day 43. A dimple-free buttock or thigh at Day 1 is precluded by the eligibility criteria. A dimple-free buttock or thigh at Day 22 and/or Day 43 does not preclude treatment of the contralateral buttock or thigh unless it is also dimple-free.

Detailed instructions for the marking and imaging of dimples will be provided in the 3-D Photography Manual.

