18.4. Study Drug Preparation

Refer to the Reconstitution Instructions for detailed preparation instructions to be used for each arm.

For each dose session the Interactive Response Technology (IRT) will assign the appropriate number of drug and diluent vials required based on the arm being dosed.

Used drug/diluent vials should be stored in a secure location until reconciled and returned by the monitor. Dispose of used needles and syringes per local regulations.

The reconstituted study drug solution should be administered as soon as possible after reconstitution. The study drug solution can be kept at room temperature for up to 4 hours following the start of the reconstitution process. If more time is needed prior to injection, refrigerate the reconstituted drug vial/syringe for up to 24 hours. Remove drug/prepared syringes from the refrigerator and allow it to stand at room temperature for 15 minutes prior to injection of study drug.

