## **3. STUDY DESIGN AND MEASURES**

### **3.1. Study Design**

This is a Phase 2a, open-label, multicenter, exploratory study to evaluate the safety and effectiveness of different injection techniques of CCH for the treatment of adult women with EFP. This study will be performed at approximately 5 sites in the United States (US).

Subjects having the evidence of cellulite in 2 buttocks or 2 thighs (treatment area) at the Screening Visit will be enrolled if they satisfy the criteria below:

- Have a CR-PCSS score of 2 (mild), 3 (moderate) or 4 (severe) as reported by the Investigator in 2 treatment areas (two thighs or two buttocks)
- Have at least 2 dimples from each treatment area that:
  - are isolated and separated by at least 5 cm from any other dimples

- score 2 or 3 on the Hexsel depression scale
- have dimple width: length ratio  $\geq 0.5$

If both buttocks and both thighs meet entry criteria for a single subject, then the thighs will be treated. No subject will be treated for EFP in both the buttocks and the thighs during this study.

The study will enroll approximately 60 subjects; 30 subjects with 2 eligible buttocks (to be dosed in the buttocks) and 30 subjects with 2 eligible thighs (to be dosed in the thighs). The 30 subjects in each treatment region (buttocks or thighs) will be assigned sequentially to 1 of 5 injection technique treatment arms on Day 1 (ie, 6 subjects per region per treatment arm). No control groups will be employed. Subjects who discontinue from the study will not be replaced.

Subjects who complete the study will participate for approximately 92 days including a 21-day of screening period, a 43-day treatment period and a 28-day follow-up period. Subjects will receive the study injections on Days 1, 22, and 43. Additional scheduled assessments will be performed on Days 4, 8, 15, and 71.

[Table 1](#) below describes the schedule of events and assessments performed during screening, treatment visits, and assessment visits.

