**Table 1: Schedule of Events (Continued)**

Procedure	Screening (Day-21 to Day -1)	Day 1	Day 4 (± 1 day)	Day 8 (± 1 day)	Day 15 (± 2 days)	Day 22 (± 2 days)	Day 43 (± 2 days)	End of Study/ Early Termination/ Day 71 (± 3 days)	Unscheduled Clinic Visit a
Study drug administration		X				X	X		
Injection site reactions/local tolerability in the treated areas		X	X	X	X	X	X	X	X
All other adverse events	←-----X-----→								

a During unscheduled visits the investigator or designee may perform any study procedure that they deem clinically necessary (eg, vital signs, clinical laboratory assessments, pregnancy test, etc).

b Performed prior to any study-required assessments.

c Should be reassessed and verified prior to study drug administration.

d Complete before and after marking injection sites.

e Complete prior to study drug administration.

f Vital signs will be collected up to 4 hours prior to, and at 15 and 30 minutes after study drug administration on Days 1, 22, and 43.

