### **3.6. Study Drug Administration**

Each subject will receive 24 injections for a total of 1.68 mg (0.84 mg per treatment area) at each treatment visit. The cumulative CCH dose will be 5.04 mg for each subject who completes the 3 treatment visits.

Each subject will receive study drug on Day 1, Day 22 and Day 43 (treatment visits) unless the treatment area is dimple-free at Treatment Visit 2 (Day 22) and/or Treatment Visit 3 (Day 43). A dimple-free buttock or thigh at Treatment Visit 1 (Day 1) is precluded by the eligibility criteria. A dimple-free buttock or thigh at Treatment Visit 2 (Day 22) and/or Treatment Visit 3 (Day 43) does not preclude treatment of the contralateral buttock or thigh unless it is also dimple-free.

The study drug, CCH, will be administered using 1 of 5 injection techniques. Each of the injection techniques are referred to as a treatment arm (I - V). Subjects will be sequentially assigned to a treatment arm at Day 1. Injection techniques differ from each other in, concentration of the CCH injectate, angle of injection, depth of injection, volume of injection and study drug administration at injection site.

At every treatment visit, irrespective of the treatment arm (injection technique) assigned, all eligible subjects will receive the same amount of study drug (CCH, 0.84mg) injected in each

assigned treatment area. All eligible subjects with dimples (in each buttock or thigh) that require treatment to improve the aesthetic appearance will receive full treatment course with CCH injections. Across all treatment arms, study drug will be administered subcutaneously while subject is in a prone position.

The injection volume and concentration for each treatment arm are outlined in [Table 2](#) below.

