### 3.6.2. Blinding and Randomization

This is an open-label study. Subjects will be sequentially assigned to a treatment arm at Day 1.

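### Arm assignment is sequential, open-label and undescribed as to concealment, so the next technique may be foreseeable and the comparison of techniques is open to avoidable selection bias

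*Protocol*

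**What the plan says.** Protocol 12.4 is headed as covering blinding and randomization. It says that the study is open-label and then: "Subjects will be sequentially assigned to Treatment Arms A to E at Day 1". SAP 3.6.2 says "This is an open-label study. Subjects will be sequentially assigned to a treatment arm at Day 1". SAP 3.1 says that the 30 subjects in each region "will be assigned sequentially to 1 of 5 injection technique treatment arms on Day 1", giving 6 per arm per region, and SAP 3.6 repeats "Subjects will be sequentially assigned to a treatment arm at Day 1". Protocol 10.1 says only that subjects are assigned to one of five arms.

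The IRT appears once, in Protocol 18.4, where "the Interactive Response Technology (IRT) will assign the appropriate number of drug and diluent vials required based on the arm being dosed". It is not described as generating or concealing the assignment.

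On dimples, Protocol 12.5 says: "Selection of dimples to be treated in the treatment areas (both buttocks or both thighs) is at the discretion of the investigator". The schedule row "Selection of 2 dimples within each treatment area for volumetric assessment" is marked at Screening and Day 1 in Protocol Section 5, but at Day 1 only in SAP Table 1. SAP 3.9 locates the measured dimple from the Day 1 image taken after marking.

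SAP 6.2 gives covariate adjustment as not applicable. The model in SAP 7.7.1.1 has arm, visit and their interaction as its fixed effects.

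**The concern.** The primary objective is the effect of CCH by injection technique, and Protocol 10.4 rules out control groups. The arm-against-arm contrast is therefore the only concurrent comparison the study offers. If site staff can foresee the next arm, they can influence, knowingly or not, who comes in for Day 1 and when. Eligible subjects run from mild to severe on the CR-PCSS, so there is room for arms to differ at baseline, and the model does nothing to correct for it.

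Dimple choice has a related gap. If the arm is known before the treated and measured dimples are settled, the choice can depend on the technique. Steering of subjects and choice of treated dimples can affect every endpoint. Choice of the two volumetric dimples affects the dimple measurements but not the whole-area Likert score.

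**Working it through.** **1. The plan's own numbers.** 5 arms × 2 regions × 6 subjects = 60, or 30 per region, which matches SAP 3.1 and 3.6.1. With about 5 sites, that is roughly 60/5 = 12 subjects per site. No power calculation is stated, so there is none to reproduce.

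**2. How often the next arm can be guessed.** The documents do not define sequential assignment. I assume a fixed five-arm rotation and compare it with random lists.

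- *Rotation visible to the site:* 100%.
- *One central rotation over S equal sites, each knowing only its own last arm.* The gap to the site's next subject is geometric with p = 1/S. The best guess is the arm after its last one, and it is right with probability p / (1 − (1 − p)^5).
  - S = 5: 0.2 / (1 − 0.8^5) = 0.2 / 0.672 = 0.297
  - S = 2: 0.5 / (1 − 0.5^5) = 0.516
  - S = 8: 0.125 / (1 − 0.875^5) = 0.257
- *Permuted blocks of 5, every earlier assignment seen:* (1/5 + 1/4 + 1/3 + 1/2 + 1) / 5 = 0.457.
- *Permuted blocks of 10 (two per arm), every earlier assignment seen:* 0.41 by simulation.
- *Central permuted blocks, 30 per region, site sees only its own assignments.* This was simulated with a guessing rule trained on the site's last five assignments.
- *Simple randomization:* 1/5 = 0.20.

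| Scheme | Sequence or all earlier assignments seen | Own site only: 2 sites | 5 sites | 8 sites |
|---|---|---|---|---|
| Fixed rotation | 100% | 52% | 30% | 26% |
| Permuted blocks of 5 | 46% | 28% | 22% | 21% |
| Permuted blocks of 10 | 41% | 27% | 22% | 21% |
| Simple randomization | 20% | 20% | 20% | 20% |

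**3. What a baseline shift would do.** This is illustration only, because the documents give no SD and the shifts are assumed. With n = 6 per arm in a region, the SE of a pairwise difference is √(2/6) = 0.58 SD. If selection moves two arms apart by b SD and there is no true difference, a nominal two-sided 5% test (the level in SAP 6.1) rejects with probability 1 − Φ(1.96 − b/0.577) + Φ(−1.96 − b/0.577), by normal approximation:

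- b = 0.25: 7.2%
- b = 0.5: 13.9%
- b = 1.0: 41.0%

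**4. Order of events on Day 1.** In the Protocol schedule, Day 1 selection of the volumetric dimples, arm assignment and marking of injection sites all carry footnote e. That footnote, worded alike in both documents, says only "Complete prior to study drug administration". It places all three before dosing but does not order them among themselves. SAP 3.9 then takes the target dimple from the post-marking image. The text therefore allows the dimples to be settled with the arm already known. Inclusion criterion 3b narrows the choice (isolated dimples, Hexsel 2 or 3, a width-to-length limit) but requires at least two such dimples per area, so discretion remains.

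**The case against.** Foreseeability is assumed rather than shown. The 100% figure needs both a fixed rotation and a site that can see it; on the central five-site reading the gap is about 30% against 22%. Who can see the sequence may be set out in the IRT specification, and Protocol 12.5 refers to a photography manual for marking instructions. The Protocol schedule begins dimple selection at Screening, before any arm is assigned, and some footnote letters differ between the two schedules as extracted. The study is an exploratory Phase 2a with no sample size estimation. Every arm gives active drug at the same dose per injection, so there is no placebo to steer away from. Baseline CR-PCSS and Hexsel scores are tabulated by arm and region (SAP 7.3). At 6 per arm, sizeable chance imbalance would remain even with randomization.

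Much of this limits the weight of the point, and the 100% figure should be read as conditional. It does not remove the point. Tabulating baseline scores shows imbalance in those scores but does not prevent it. Randomization leaves chance imbalance, which the confidence intervals are meant to reflect; selection bias is not covered by them. Settling eligibility before assignment (Protocol 11.1) does not hide the next arm. The blinded central Likert read limits assessment bias, not who or what enters each arm. The Protocol schedule still allows dimple selection on Day 1 with no order relative to assignment. If a concealed random list was intended, the text should say so.

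**Conclusion.** The concern holds. As written, the only between-technique comparison is non-random and has no described concealment, and the model does not adjust for baseline. If the sequence is a fixed rotation, the next arm can be guessed between about 26% (central, 8 sites) and 100% (visible to the site) of the time. The reference figures are 21% to 28% for central permuted blocks over 8 to 2 sites and 20% for simple randomization. These rest on the rotation assumption, equal sites and the stated views of the sequence. The documents do not allow the bias itself to be sized. Because the study is exploratory, this weakens the technique comparison rather than invalidating it, and it is worth fixing because the remedy is cheap.

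**What to change.** - **Allocation.** In Protocol 12.4 and SAP 3.1, 3.6 and 3.6.2, replace sequential assignment with random 1:1:1:1:1 assignment to the five arms through the IRT, from a centrally held, concealed list in permuted blocks within region. With 30 per region, 6 blocks of 5 or 3 blocks of 10 keep 6 per arm.
- **Day 1 order.** Add one rule: the IRT releases the arm only after the two target dimples per area and the Day 1 dimples to be treated are recorded.
- **Schedules.** State in both when the two volumetric dimples become final, and reconcile Screening plus Day 1 (Protocol) with Day 1 only (SAP).
- **Labels.** While editing, reconcile arms A to E in Protocol 12.4 with Treatments I to V elsewhere.
- **If subjects have already been assigned.** The SAP revision is dated 11 February 2019 and the synopsis estimated last completion in January 2019. If assignment is done, do not describe it as random. State how the sequence was run and who could see it, and report this as a limitation.

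The cost is one list in the IRT already used for vials, a wording change, one ordering rule and the IRB approval that Protocol 21.1 requires for an amendment. No extra subjects, visits or staff are needed.
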